10.1.1.2 Unexpected Adverse Drug Reaction

An “unexpected” adverse drug reaction is an adverse reaction, the nature or severity of which is not consistent with the applicable product information (e.g. Investigator’s Brochure for drugs that are not yet approved and Product Information for approved drugs, respectively). [ICH E2A]

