2.2 Categorisation of study

Interventional study with investigational medicinal product (IMP) for intralymphatic allergen immunotherapy. Clinical trial, Risk category B.

Allocation to Risk Category B because of off-label use of the allergen, i.e., intralymphatic administration and dosage change of investigational medicinal product (IMP).

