3.2 Investigational Product (treatment) and Indication

Polvac™ Grass+Rye, a grass- allergen extract with microcrystalline tyrosine (MCT) adjuvant for treatment of allergic rhinitis will be used. The active ingredient is a standardized grass pollen allergen extract from 13 species of grass combined with the excipient MCT adjuvant as from Allergy Therapeutics Ltd (cf. Appendix 001 for further details). The allergen extract has been treated with glutaraldehyde as to reduce allergic side effects, i.e., to increase the safety. Bencard AG (Greifensee, Switzerland) is providing the product in Switzerland. Polvac™, is a marketed product that has been approved by the Swiss medical product agency *Swissmedic* (#46489 and #65479) and adheres to GMP. The product consists of needle-like crystalline structures of an average size of 20 micrometers (15). Polvac™ is approved for SCIT, which includes 6 pre-seasonal injections with 1-2 week intervals for 3-4 years, adding up to a total of 18 to 24 injections for the treatment to be completed (16-18). In the current study, for SCIT, Polvac™ will be used as described by the provider (Appendix 001). For ILIT, the samples will be processed as described by the provider, but administered at one fifth of the dose used for SCIT.

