3.7 Risks / Benefits

Benefits

- The study should improve our understanding of the immune responses stimulation after SCIT and ILIT, and could lead to novel developments in AIT, and especially, ILIT.
- All study participants will get one additional AIT injection (SCIT or ILIT), which may contribute to and even further consolidate the success of their therapy.
- Results from previous studies suggest that an ILIT injection on top of a full SCIT cycle may further improve the therapeutic efficacy.

- The study participants receiving an ILIT injection would get to know a new route of AIT. In the future, they may use this as basis for discussion with their treating allergist regarding a possible change in the treatment regimen, as an alternative to SCIT. The benefits being reduced treatment times and lower allergen doses with potentially less AIT-associated side effects.

Risks

The SmPc for Polvac™ is the reference sheet for evaluation of AEs (see Appendix 002). The following known SCIT-associated are mentioned

- AE: itch or swelling and rubor at the injection site that resolves without treatment by next day (27%, 125 events in 462 injections of 154 patients)
- AE: allergic symptoms - urticaria, tightness of chest, drop in FEV1 >40% (2%, 11 of 462 injections) treated with an antihistamine or a short acting beta-2 agonist. Every clinic offering AIT is equipped to deal with this AE, and patients are required to stay in the clinic for 60 minutes for observation to deal with these incidents.
- Unexpected AE: some few patients reported fatigue within 6 hours
- Severe AE: systemic allergic symptoms that required hospitalization: drop in blood pressure, generalized urticaria or deterioration by 40% of peak flow or FEV1 (0.2%, 1 of 462 injections)
- Generation of autoimmune antibodies may be a potential long-term effect of AIT. This has not been reported in any of the AIT trials with Polvac™.
- One study reported one patient with hypothyroidism with auto-antibodies among 72 patients treated by ILIT (patients were not treated with Polvac™ but with a comparable alum-based product).
- In all AIT procedures (ILIT, SCIT or SLIT), there is a risk of anaphylactic reactions that typically happens within minutes of the injections. This is a SAE that will required hospitalization.

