10.1.2 Reporting of SAE and other safety related events

10.1.2.1 Reporting of SAEs

The study doctor or the principal investigator will report all SAEs immediately and within a maximum of 24 hours to the Sponsor of the study (via notification by phone/email) The Sponsor will re-evaluate the SAE and return the form to the site.

The study doctor or the PI will report SAEs resulting in death to the Ethics Committee via BASEC within 7 days. The sponsor-representative will inform all SAEs to *Swissmedic* within 7 days of the event.

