10.1.2.5 Periodic reporting of safety

The ASR / Development safety update report (DSUR) is written in compliance to ICH Harmonised Guideline E2F for commercial and non-commercial sponsor.

An ASR / DSUR is submitted once a year to the IEC via Investigator and to Swissmedic via Sponsor.

The start date for the ASR/DSUR is the date the sponsor's first authorisation to conduct a clinical trial.

The ASR / DSUR is submitted to the IEC and to Swissmedic throughout the duration of the clinical trial, and the last ASR / DSUR submission will cover the Last Patient Last Visit.

The sponsor will submit an annual report of SUSAR and SAE to *Swissmedic* as well as to the Pharmacovigilance department of the medicine supplier Allergy Therapeutics.

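### The only reference named for adverse events is the SmPC of a subcutaneous product, so a non-fatal serious reaction of a listed type after off-label ILIT would be classed as expected and could miss expedited reporting to the ethics committee

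*Combined protocol and SAP*

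**What the plan says.** **Expectedness.** Section 10.1.1.2 defines an unexpected reaction as one "the nature or severity of which is not consistent with the applicable product information". It gives as examples of the reference the "Investigator’s Brochure for drugs that are not yet approved and Product Information for approved drugs, respectively". Under section 10.1.1.3, an event becomes a SUSAR if it is related, serious and unexpected.

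**Reference document.** Section 3.7 states: "The SmPc for Polvac™ is the reference sheet for evaluation of AEs (see Appendix 002". It makes no distinction by route. The list of events that follows is introduced with "The following known SCIT-associated are mentioned".

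**Status of the two routes.** Section 3.2 says "Polvac™ is approved for SCIT, which includes 6 pre-seasonal injections with 1-2 week intervals". Section 2.2 gives the off-label intralymphatic route and the changed dosage as the reason for risk category B.

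**Reporting.** For SAEs in general, section 10.1.2.1 says: "The study doctor or the PI will report SAEs resulting in death to the Ethics Committee via BASEC within 7 days". The same section has every SAE go to Swissmedic within 7 days, whatever its expectedness. Under section 10.1.2.2, SUSARs go to both bodies, within 7 days if fatal and 15 days otherwise. Section 10.1.2.5 adds: "An ASR / DSUR is submitted once a year to the IEC via Investigator and to Swissmedic via Sponsor".

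**The concern.** Expectedness is normally judged against reference safety information that covers the way the product is used in the trial. Here the one document named belongs to the subcutaneous product, and no section names a reference for the intralymphatic arm. The simplified product dossier mentioned in section 8.1.3 is not given that role.

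This matters because the reaction of most interest after an allergen injection, a serious systemic allergic reaction, is already on the list in section 3.7. The test in section 10.1.1.2 looks at nature and severity and not at frequency. A reaction that matches the list would therefore stay expected even if it occurred more often after ILIT than after SCIT.

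What is at stake is timely notice to the ethics committee about the experimental route. There is no data safety monitoring committee (section 1.6) and no statistical stopping criterion (section 11.3). The protocol's own experience at 400 U intralymphatically is four patients treated off-label, who reached that dose by escalation (sections 3.5 and 8.3).

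**Working it through.** **1. The plan's own rates (section 3.7).** These reproduce:
- local reactions: 125/462 = 27.1% (stated 27%)
- allergic symptoms treated with an antihistamine or a bronchodilator: 11/462 = 2.4% (stated 2%)
- systemic reactions with hospital admission: 1/462 = 0.22% (stated 0.2%)

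**2. Applying the rule to one case.** Take a non-fatal systemic reaction after ILIT with a fall in blood pressure and admission to hospital, judged related.
- Serious? Yes, because of the admission (10.1.1).
- Reference? The Polvac SmPC (3.7; product information for an approved drug, 10.1.1.2).
- Consistent in nature and severity with what is listed? Yes, going by the list in 3.7.
- Result: expected, and not a SUSAR under 10.1.1.3.

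**3. Who hears of it, and when.**

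| Recipient | Route | Timing |
|---|---|---|
| Sponsor | 10.1.2.1 | 24 hours |
| Swissmedic | 10.1.2.1, all SAEs | 7 days |
| Ethics committee | 10.1.2.1, fatal SAEs only | does not apply |
| Ethics committee | 10.1.2.2, SUSARs only | does not apply |
| Ethics committee | 10.1.2.3, if immediate safety measures had to be taken | 7 days |
| Ethics committee | 8.5, if a treated patient decides to discontinue | 24 hours |
| Ethics committee | 2.3, if the trial is interrupted or stopped early | 15 days |
| Ethics committee | 10.1.2.5, annual report | yearly |

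Section 2.5 also mentions interim reports but gives neither content nor dates. After a single injection, a patient who has reacted has no further study dose to decline, so the route in 8.5 need not be triggered.

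**4. Timing of the annual report.** The reporting year starts at first authorisation (10.1.2.5). Assume that this is no earlier than the date of protocol version 2, 30.05.2023, since section 2 still awaits approval. If the first report is due one year later, that is 30.05.2024 or after. The date of the last injection depends on which section is used:
- 9.3.2: by 03.02.2024, which is 117 days before 30.05.2024
- 9.3.5: day 28 by 31.03.2024, so injection by 03.03.2024, which is 88 days before
- 9.3.4: day 7 by 24.03.2024, so injection by 17.03.2024, which is 74 days before

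On each reading, the first annual report would come after all 15 ILIT patients had been injected.

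**5. How likely such an event is.** With 15 ILIT injections (8.1) and a rate r per injection, P(at least one) = 1 − (1 − r)^15.
- r = 1/462: 1 − (461/462)^15 = 3.2%
- r = 1.20%, the exact (Clopper-Pearson) 95% upper limit for 1/462: 1 − 0.988^15 = 16.6%

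Both figures carry the listed rate over to ILIT, which is an assumption. The four patients at 400 U cannot replace it. If none of them had a serious reaction, the one-sided 95% upper limit is 1 − 0.05^(1/4) = 53%.

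**The case against.** The strongest reply is that the gap is narrow, and much of this stands.

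- **Expedited reporting is not lost altogether.** A reader might infer that the early signal is switched off for ILIT. It is not: the sponsor hears within 24 hours and Swissmedic within 7 days, which is faster than the 15 days for a non-fatal SUSAR. Only the ethics committee is affected, and sections 2.3, 8.5 and 10.1.2.3 may still bring it in.
- **ILIT reactions can still be SUSARs.** A reader might infer that a serious ILIT reaction can never qualify. Section 10.1.1.2 tests severity as well as nature, and 10.1.1.3 requires each SAE to be evaluated. A reaction worse than those listed, or of another kind, still qualifies.
- **The wording leaves some room.** Section 10.1.1.2 speaks of applicable information and gives its reference documents as examples. No sentence says that a listed reaction by an off-label route must be expected. That is true, but section 3.7 names a single reference and offers the assessor no other.
- **The reaction is foreseen for ILIT.** Section 3.7 names anaphylaxis as a risk of every immunotherapy route. Section 3.4 reports published ILIT trials and 90 injections in the active group of the ongoing in-house trial without severe adverse events. However, that trial used 133 U (8.3) and is still blinded. Foreseeing a reaction is also not the same as defining a reference for this route.
- **The size should not be inflated.** Assumed rates of 5% or 10% would give 54% or 79% for 15 injections, but they are about 23 and 46 times the listed rate and nothing in the documents supports them.
- **Unseen appendices.** The SmPC and the simplified dossier are not available here, so the listed terms are known only through section 3.7. The denominator there, 462/154 = 3.0 injections per patient, fits the three-injection ILIT course in section 3.4 better than the six-injection cycle in 3.2. The source and route of these rates are therefore uncertain, although the protocol labels them SCIT-associated.

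**Conclusion.** The point holds in a limited form. Because section 3.7 names one reference for both routes, a non-fatal serious systemic reaction after ILIT that resembles the listed SCIT-associated reactions would be classed as expected. It would then not reach the ethics committee as a SUSAR. Swissmedic would know within 7 days. The committee might learn of it only from the annual report, after the last ILIT injection, unless one of the conditional routes applied.

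The illustrative chance that the case arises among 15 ILIT injections is 3.2%, or 16.6% at the upper limit. This rests on carrying 1/462 over to ILIT; the true rate at 400 U is not documented. The timing rests on authorisation no earlier than 30.05.2023 and a first report one year later.

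A reader might also infer that a SUSAR count by arm would come out at zero for ILIT and be taken as evidence of safety. The documents do not support that: section 11.4 plans no such count, safety is assessed through local and systemic reactions (5.4), and all AEs and SAEs are recorded (10.1). This is a worthwhile and inexpensive correction to the reporting rules, not a failure of safety oversight as a whole.

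**What to change.** In section 10.1.1.2, limit the SmPC as the reference for expectedness to the SCIT arm, and align the sentence in section 3.7. Then add one of two rules for ILIT:
- SAEs judged related to the intralymphatic injection are handled as unexpected for reporting purposes and follow section 10.1.2.2; or
- such SAEs go to the ethics committee on the same 7-day timeline as to Swissmedic. This leaves the definition of unexpected as it stands.

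In the same edit, state the source and route of the rates in section 3.7. Also reconcile the citation of the simplified dossier as Appendix 003 (8.1.3) with the appendix list, where that number is the rescue medication.

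The cost is one or two sentences on reporting and at most a few extra expedited reports among 15 patients. Some of those could concern anaphylaxis, which the protocol already names as a risk of ILIT. No dose, schedule, treatment or analysis changes.

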10.1.1.3 Suspected Unexpected Serious Adverse Reactions (SUSARs)

The Principle-Investigator evaluates any SAE that has been reported regarding seriousness, causality, and expectedness. If the event is related to the investigational product and is both serious and unexpected, it is classified as a SUSAR.

10.1.1.4 Assessment of Severity

For all AEs, serious as well as non-serious, the investigator must make an assessment of severity:

- Mild: awareness of sign or symptom, but easily tolerated and cause no interference with daily activities.
- Moderate: discomfort enough to cause interference with daily activities.
- Severe: inability to perform normal daily activities.

10.1.2 Reporting of SAE and other safety related events

10.1.2.1 Reporting of SAEs

The study doctor or the principal investigator will report all SAEs immediately and within a maximum of 24 hours to the Sponsor of the study (via notification by phone/email) The Sponsor will re-evaluate the SAE and return the form to the site.

The study doctor or the PI will report SAEs resulting in death to the Ethics Committee via BASEC within 7 days. The sponsor-representative will inform all SAEs to *Swissmedic* within 7 days of the event.

10.1.2.2 Reporting of SUSARs

A SUSAR will be reported by the principal investigator to the Ethics Committee via BASEC and to Swissmedic by the Sponsor within 7 days, if the event is fatal, or within 15 days (all other events).

10.1.2.3 Reporting of immediate safety and protective measures

All suspected new risks and relevant new aspects of known adverse reactions that require immediate safety-related measures, are reported by the study doctor to the Sponsor within 24 hours.

The principal investigator will notify the Ethics Committee and the sponsor will notify the *Swissmedic* within 7 days if immediate safety and protective measures had to be taken during the trial conduct. The circumstances necessitating the safety-protective will also be reported.

10.1.2.4 Reporting and handling of pregnancies

Before the allergen injection a pregnancy testing (if applicable) is performed. Pregnant participants are excluded from the clinical study. All interventions except one blood sampling (28 days) are done on the day of pregnancy testing.

Any pregnancy within 28 days after allergen injection will be reported to the Sponsor within 24 hours. The course and outcome of the pregnancy should be followed up carefully, and any abnormal outcome regarding the mother or the child should be documented and reported.

10.1.2.5 Periodic reporting of safety

The ASR / Development safety update report (DSUR) is written in compliance to ICH Harmonised Guideline E2F for commercial and non-commercial sponsor.

An ASR / DSUR is submitted once a year to the IEC via Investigator and to Swissmedic via Sponsor.

The start date for the ASR/DSUR is the date the sponsor's first authorisation to conduct a clinical trial.

The ASR / DSUR is submitted to the IEC and to Swissmedic throughout the duration of the clinical trial, and the last ASR / DSUR submission will cover the Last Patient Last Visit.

The sponsor will submit an annual report of SUSAR and SAE to *Swissmedic* as well as to the Pharmacovigilance department of the medicine supplier Allergy Therapeutics.

10.1.3 Follow up of AEs and SAEs

Most allergic events are resolved within a week, and we do not expect to have to follow patients for longer. If an adverse event is registered in a patients CRF this will be addressed by attending staff at the next visit. Patients will be able to contact staff by e-mail during the trial. If a patient should experience allergic symptoms severe enough to warrant hospitalization this will be recorded in the CRF.

10.2 Assessment, notification and reporting on the use of radiation sources

Not applicable.

11. STATISTICAL METHODS

11.1 Hypothesis

This study is a pilot study which goal is to describe the effect of ILIT on the immune cell composition and immune cell function in lymph nodes and in blood. We will compare this with the effect SCIT on the same, but not to confirm a hypothesis of a certain difference.

We will use a wide screening with several methods to describe the immune responses.

11.2 Determination of Sample Size

Not applicable for a pilot study.

11.3 Statistical criteria of termination of trial

There is no statistical criteria for stopping the study.

11.4 Planned Analyses

The investigators and the appointed statistician will be responsible for the statistical analysis of the collected data. The statistical software used will be Graph Pad Prism®, SPSS®, or open-source software “R”.

We will apply descriptive statistics to describe frequencies, proportions and numbers for the various analysis to be performed. The data will be described with an average (mean or median) and with variances (confidence intervals or standard deviations or standard errors) depending on the type of data.

Data will typically be illustrated with scatter plots or with box plots with 90 and 10% whiskers. For multiparametric analysis, the results from different tests will be transformed/normalized (e.g. z-score normalization) to generate heat maps, and for the hierarchical clustering of treatments and phenotypes, we will apply The R Project with Euclidean metrics.

For comparative testing of the different treatment groups (SCIT versus ILIT), ANOVA is applied for continuous parametric data that fulfil the criteria for ANOVA. Kruskal-Wallis analysis are applied for non-parametric ranked data.

For changes over time within patients, dependent (paired) t-test may be used. No sex/gender difference analysis is planned.

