Objective(s):	The study seeks primarily to determine hallmarks in immunological responses (analysis of inflammatory cell and proteins) in lymph nodes and in peripheral blood after allergen ILIT and SCIT.
Outcome(s):	
 1) Fine needle aspiration (FNA) material of lymph node tissue at baseline and 2 or 6 or 24 hours after allergen ILIT or SCIT will be evaluated for changes in cell populations and cell functions. 2) Immunological changes (analysis of cell populations and functions ex vivo and in vitro) in peripheral blood at baseline, after 2 or 6 or 24 hours, after 7 days and after 28 days of allergen ILIT or SCIT.

Study design:	
This is a prospective, comparative, clinical study. We will recruit 30 grass-pollen allergic patients undergoing pre-seasonal short-term SCIT scheme with Polvac™ Grass+Rye at the USZ Allergy Unit. 4 weeks after last SCIT injection and after reaching maintenance SCIT dose (2000 U), the patients will receive an additional allergen injection as part of the study. Patients will be randomized into the 3 different groups with 10 participants per group. Patients will receive a single ultrasound-guided injection with Polvac™ Grass+Rye ILIT (0.1 ml, 400 U) or SCIT (0.5 ml, 2000 U).
 
FNA of lymph node tissue will be conducted at baseline and at 2, 6 or 24 hours after allergen injection. Venous blood will be sampled at baseline, after 2, 6 or 24 hours, after 7 days, and after 28 days of allergen injection.

Inclusion / Exclusion criteria:	
Included are patients between 18 and 55 years of age with grass-pollen allergy and undergoing pre-seasonal short-term-scheme Polvac™ Grass+Rye SCIT at the USZ Allergy Unit for treatment of allergic rhinoconjunctivitis.
 
Exclusion criteria are significant allergy to house dust mite or pet animal allergens, uncontrolled asthma, upper airway disease, severe pulmonary disease, recent allergic reactions, immunosuppression, cardiovascular disease, malignant disease, conspicuous lymph node size or morphology, use of ACE-blockers and any other diseases or conditions rendering the treatment of anaphylactic reactions difficult.

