7.3 Assignment to study groups

The 30 patients will be randomized to the two different equally-sized treatment groups (ILIT 400 U and SCIT 2000 U), with each 15 patients per group.

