8.2.1.3 Blood collection and preservation of cells and blood serum

First venous blood collection is performed at baseline before the immunotherapy. Second blood collection is performed 2, 6 or 24 hours post injection. Third and fourth blood collection are performed 7 and 28 days after immunotherapy. Each time, 25 ml venous blood is collected for preparation of PBMCs and 5 ml blood is collected for preparation of serum. Both samples are processed by routine in-house methods within 2 hours for preparation of serum and cells. The produced serum is aliquoted in 1 ml samples and frozen at – 20 °C for later analysis. Whole blood is centrifuged on Ficoll and the PBMCs isolated and washed in PBS before re-suspended in DMSO-containing live cell freezing medium. 1 ml aliquots of the cells are slow-frozen in cryotubes and finally stored at -80 °C before further analysis.

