8.7 Concomitant Interventions (treatments)

Besides the allergen administration (via ILIT or SCIT), the FNA (2x) and blood collection (4x) a pregnancy test, 2x peak flow measurement and a physical examination will be performed.

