9.2 Assessments of outcomes

9.2.1 Assessment of primary outcome

FNA material of lymph node tissue at baseline and 6 hours after allergen injection (via ILIT or SCIT) will be evaluated for changes in lymph node cell populations and cell culture expression patterns.

Immunological changes (analysis of cell populations and cell cultures) in peripheral blood at baseline, after 2, 6 and 24 hours and at 7 and 28 days after allergen injection (via ILIT or SCIT).

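### Section 11.4 names no baseline or sampling-hour adjustment for the SCIT–ILIT comparison of blood readouts; adding it is cheap and may narrow the interval, depending on a correlation the documents do not give

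*Combined protocol and SAP*

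**What the plan says.** - **Between-arm test (Section 11.4).** "For comparative testing of the different treatment groups (SCIT versus ILIT), ANOVA is applied for continuous parametric data that fulfil the criteria for ANOVA". Kruskal-Wallis is named for ranked data. No covariate or second factor is named, and the response variable is not defined.
- **Within-patient test (Section 11.4).** "For changes over time within patients, dependent (paired) t-test may be used". This is optional and does not compare the arms.
- **Pre-injection blood (Section 8.2.1.3).** "First venous blood collection is performed at baseline before the immunotherapy". The Visit 2 procedures in Section 9.3.2 confirm it.
- **Early blood (Section 8.2.1.3).** "Second blood collection is performed 2, 6 or 24 hours post injection". Sections 5.1 and 6.1 also give one hour out of three. Section 9.2.1 differs: "in peripheral blood at baseline, after 2, 6 and 24 hours and at 7 and 28 days after allergen injection".
- **Number of collections (Section 8.7).** Four blood collections per patient.
- **Arms (Section 7.3).** "The 30 patients will be randomized to the two different equally-sized treatment groups", with 15 patients each. Section 6.2.1 describes randomisation to arm only; nothing says how a patient's sampling hour is assigned.
- **Status.** Section 4.2 makes the ILIT–SCIT comparison the primary objective. Section 11.1 says the study is not meant to confirm a particular difference, and Section 11.2 gives no sample-size calculation.

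**The concern.** Two likely sources of spread in a blood readout are recorded for every patient: the patient's own level before injection and, for the early sample, the hour of sampling. A one-factor ANOVA or a Kruskal-Wallis test on post-injection values leaves both in the error term. The paired t-test does not fill the gap, because a significant change in one arm and not in the other does not show that the changes differ.

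Because the response is not named, post-injection value or change could also be chosen readout by readout after the data are seen. That choice affects precision: at a low pre/post correlation a change score is less precise than ignoring baseline altogether.

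At stake is the width of the interval around each ILIT–SCIT difference in a study of 30 patients whose results are to guide larger ones (Section 3.1). Validity is not at stake.

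**Working it through.** The plan states no SD, effect size, alpha or power, so there is no figure to reproduce.

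**Inputs.** From the documents: 15 per arm (Sections 3.5, 6.1, 7.3 and 8.1), one pre-injection sample, one early sample, and samples on days 7 and 28. The synopsis instead has three groups of 10; that is a separate inconsistency. Assumed: SD 1 before and after injection, two-sided 5%, a true difference of 1 SD for power, and r (the correlation of pre- and post-injection values) of 0, 0.3 or 0.6.

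**Days 7 and 28.** Half-width = t × √(variance factor × 2/15). The variance factors are:
- post-injection value only: 1, with 28 df (t = 2.048);
- change score: 2(1 − r), with 28 df;
- baseline-adjusted: (1 − r²)(1 + 1/26), with 27 df (t = 2.052).

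Examples:
- post only: 2.048 × √(2/15) = 2.048 × 0.365 = 0.748;
- adjusted, r = 0.6: 2.052 × √(0.64 × 1.038 × 0.1333) = 2.052 × 0.298 = 0.611;
- change, r = 0.3: 2.048 × √(1.4 × 0.1333) = 2.048 × 0.432 = 0.885.

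| Analysis | r | Half-width, formula (SD) | Half-width, simulated (SD) | Simulated power for 1 SD |
|---|---|---|---|---|
| Post only | any | 0.75 | 0.74 | 75–76% |
| Change | 0.3 | 0.88 | 0.88 | 61% |
| Change | 0.6 | 0.67 | 0.66 | 84% |
| Adjusted | 0 | 0.76 | 0.76 | 74% |
| Adjusted | 0.3 | 0.73 | 0.72 | 77% |
| Adjusted | 0.6 | 0.61 | 0.61 | 90% |

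Simulation used 20,000 trials per setting. Its half-widths are slightly smaller because the average standard error lies a little below the square root of the variance. Setting the adjusted half-width equal to 0.748 gives a break-even r of about 0.20. With no true difference, all three analyses rejected in 4.8–5.3% of trials.

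**Early sample, one hour per patient.** Suppose hours are even within arm (5/5/5) and the readout shifts by s SD from one hour to the next. Without an hour term, the expected residual variance is (28 + 20s²)/28. The post-only half-width is then 2.048 × 0.365 × √((28 + 20s²)/28):
- s = 0.25: 0.76;
- s = 0.5: 0.81 (simulated 0.80);
- s = 1: 0.98 (simulated 0.97).

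With baseline and hour in the model the half-width is 0.73 at r = 0.3 and 0.61 at r = 0.6, whatever s is.

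**Worst case.** Take r = 0, no hour effect, and hours unbalanced between arms because they are assigned at random. Three useless terms give a variance factor of about 1 + 3/24 = 1.125 with 25 df. The standard error is √(1.125 × 0.1333) = 0.387, and power for 1 SD is 70%, against 75–76% unadjusted. Simulation also gives 70%.

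**Single-hour contrasts.** About 5 against 5 gives 2.064 × √(2/5) = 1.31 SD (24 df), too wide for more than description.

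**Sampling times.** Baseline, one early sample, day 7 and day 28 make four collections, which matches Section 8.7. All three early hours would make 1 + 3 + 2 = 6, which does not. Section 9.2.1 is therefore the odd one out, but it is the section that defines assessment of the primary outcome.

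**The case against.** The strongest reply is that this is a descriptive pilot with no primary endpoint, no hypothesis and no sample-size calculation, so the choice between ANOVA and a covariate-adjusted model is a refinement. That stands as to weight. It does not remove the point, because Section 11.4 itself plans comparative tests between the arms.

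The gain is also not assured. It depends on r, will differ between readouts, is small at r = 0.3, and is slightly negative below about 0.2. The larger early-sample gains need a marked shift between hours: s = 1 means 2 SD between 2 and 24 hours. All of this stands.

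Four stronger readings are tempting, and the documents do not support them.
- **A reader might infer that the plan ignores baseline between arms.** Section 11.4 is silent on the response, and the synopsis and Sections 5.1 and 9.2.1 speak of changes. ANOVA on change is a fair reading; the gain at r = 0.6 is then only from 0.66 to 0.61 SD, though at r = 0.3 it is from 0.88 to 0.72–0.73.
- **A reader might infer inflated false positives**, by taking Section 9.2.1 to mean three early samples per patient analysed as independent rows. No section proposes that analysis, and the other sections point to one early sample.
- **A reader might extend baseline adjustment to lymph nodes.** They have no pre-injection value: Section 6.1 has the contralateral node aspirated at the same time as the treated node.
- **A reader might take a rank model as supplying the interval as well.** Its coefficient is not a difference on the readout's scale.

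**Conclusion.** The point holds as a cheap improvement to the blood analysis, not as an error in the plan. Section 11.4 leaves the response undefined and names neither the pre-injection value nor the sampling hour. With 15 per arm, adjustment takes the day 7 and day 28 half-width from about 0.74 SD (post-injection values) to 0.72–0.73 SD at r = 0.3 and 0.61 SD at r = 0.6, and it is more precise than a change score at both values. The possible loss is bounded: about 2 points of power at r = 0, and about 6 points (76% to 70%) if an unneeded hour term is added and hours are unbalanced.

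These sizes rest on an assumed SD of 1, equal spread before and after injection, a 1 SD effect for the power figures, 30 complete patients and an assumed r. The hour model also assumes that the arm difference is the same at each hour. The textual part, that no covariate and no response variable are named, rests on no assumption.

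**What to change.** In Section 11.4, for blood readouts only:

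1. For each continuous readout (log scale if skewed), fit a linear model of the post-injection value on arm and the pre-injection value. Report the ILIT–SCIT difference with a 95% confidence interval.
2. For the early sample, add sampling hour as a factor. Keep arm contrasts within a single hour descriptive.
3. Where ranks are needed, use a baseline-adjusted rank model for the test only, and report the effect separately on the readout's scale.
4. Keep the paired t-test as a within-patient description.

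Before fixing the early-sample model, reconcile the blood times in Section 9.2.1 with Sections 5.1, 6.1, 8.2.1.3 and 8.7, and state how hours are allocated.

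The cost is a few sentences and modest work in R, which the plan already names; no new visit or sample is needed. Besides the small loss of power where r is low, a patient without a pre-injection sample drops out of the adjusted model, since Section 11.5 rules out imputation.
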